9.7.5 ADVERSE EVENT REPORTING

All clinically important AEs as described in **Section 9.7.4**, will be recorded in the StudyTRAX database. For each AE, an email will be sent to the DCC, site PI, and blinded physician adjudicating AEs at each site. AEs will be summarized using System Organ Class and preferred terms. Tables will show by treatment group the number and percentage of participants experiencing an AE within a System Organ Class or within preferred term category by severity or by relationship to study product. For the calculations in these tables, a participant with

multiple AEs within a category will be counted once under the maximum severity or the strongest recorded causal relationship to study product. Formal statistical testing comparing groups is not planned since interpretation of differences must rely heavily upon clinical judgment.

The DSMB will review all AEs during scheduled interim analyses. The DCC will distribute the written summary of the DSMB's periodic review of adverse events to investigators for submission to their respective IRBs.

9.7.6 SERIOUS ADVERSE EVENT REPORTING

Site investigators will report all **serious AND unexpected adverse events or reactions**, regardless of relationship to the study intervention to the DCC by phone, fax, or email within 24 hours of becoming aware of the event. The site investigator should include an assessment of whether there is a reasonable possibility that the study intervention caused the event.

Investigators will also report all **serious AND administration related adverse events** (as described in **Section 7.1.8**) to the DCC by phone, fax or email within 24 hours of becoming aware of the event.

The DCC will review the event and may inform the site to permanently discontinue study drug administration to the subject (**Section 7.1.8**), and may hold enrollment pending Scientific Review Committee (SRC) and DSMB review (**Section 11.1.5**). The local IRBs will also be notified according to local requirements. The investigator will then submit a detailed written report to the DCC and the IRB no later than 7 calendar days after the investigator discovers the event.

The DCC will report all **unexpected and study-related deaths or life-threatening suspected serious adverse events (SUSAR)** to the FDA within 7 calendar days. The DCC will report **all deaths occurring during the study hospitalization and all serious, unexpected, and study-related adverse events and all administration related adverse events** to the DSMB, by email, or telephone, within 7 calendar days of the DCC being notified of the event. A written report will be sent to the DSMB and the FDA within 15 calendar days, and these reports will be sent to investigators for submission to their respective IRBs. The DSMB will also review all adverse events during scheduled interim analyses. The DCC will distribute the written summary of the DSMB's periodic review of adverse events to investigators for submission to their respective IRBs.

9.8 UNANTICIPATED PROBLEMS

9.8.1 DEFINITION OF UNANTICIPATED PROBLEMS (UP)

The USAMRMC Human Research Protection Office (HRPO) considers unanticipated problems involving risks to participants or others to include, in general, any incident, experience, or outcome that meets **all** of the following criteria:

- Unexpected, in terms of nature, severity, or frequency, given the research procedures that are described in the protocol-related documents, such as the IRB-approved research protocol, the Investigator's Brochure, or the informed consent document; and the characteristics of the subject population being studied;
- Related or possibly related to participation in the research, in this guidance document, possibly related means there is a reasonable possibility that the incident, experience, or outcome may have been caused by the procedures involved in the research;
- Suggests that the research places subjects or others at a greater risk of harm (including physical, psychological, economic, or social harm) than was previously known or recognized.

9.8.2 UNANTICIPATED PROBLEM REPORTING

Site investigators will report unanticipated problems (UPs) to their reviewing IRB as well as to the DCC and the lead PI. The UP report will include the following information:

- Protocol identifying information: protocol title and number, site investigator's name, and the IRB project number;
- A detailed description of the event, incident, experience, or outcome;
- An explanation of the basis for determining that the event, incident, experience, or outcome represents an UP;
- A description of any changes to the protocol or other corrective actions that have been taken or are proposed in response to the UP.

To satisfy the requirement for prompt reporting, UPs will be reported using the following timeline:

- All UPs will be reported to the IRB and to the DCC/PI within 24 hours of the investigator becoming aware of the event.

All UPs should be promptly reported to HRPO by [contact]), or by [contact]). A complete written report will follow the initial notification. In addition to the methods above, the complete report can be sent to the US Army Medical Research and Materiel Command, ATTN: MCMR-RP, [name].

10 STATISTICAL CONSIDERATIONS

10.1 STATISTICAL HYPOTHESES

- **Primary Safety Endpoint:**

The primary safety endpoint is to evaluate the safety of inhaled CO, by determining COHb levels and the incidence of pre-specified administration-related AEs.

- Safety of inhaled CO, defined by the incidence of pre-specified administration-related AEs (as defined below) and spontaneously reported AEs through study day 7.
 - Acute MI within 48 hours of study drug administration
 - Acute CVA within 48 hours of study drug administration
 - New onset atrial or ventricular arrhythmia requiring DC cardioversion within 48 hours of study drug administration
 - Increased oxygenation requirements defined as: an increase in FiO_2 of ≥ 0.2 **AND** increase in $\text{PEEP} \geq 5$ cm H_2O within 6 hours of study drug administration
 - Increase in COHb $\geq 10\%$
 - Increase in lactate by ≥ 2 mmol/L within 6 hours of study drug administration

Hypothesis: We hypothesize that low dose iCO will be safe and well-tolerated in patients with ARDS.

- **Primary Efficacy Endpoint:**

The primary efficacy endpoint is to compare the effects of iCO versus placebo on mtDNA levels from baseline to day 5 (or death, whichever comes first) in patients with ARDS.

Hypothesis: We hypothesize that, compared to placebo, low dose iCO will lead to a reduction in mtDNA levels on day 5 compared with baseline.

- **Secondary Efficacy Endpoints:**

The secondary endpoints will examine the effects of iCO versus placebo on the following outcomes:

- Lung Injury Score (LIS) on days 1-5, and 7
- PaO₂/FiO₂ ratio on days 1-5, and 7
- Oxygenation Index (OI) on days 1-5, and 7
- Dead Space Fraction (Vd/Vt) on days 1-3, and 7
- Sequential Organ Failure Assessment (SOFA) score on days 1-5, 7, 14, 28

Hypothesis: We hypothesize that low dose iCO will reduce the severity of lung injury and non-pulmonary organ failure in patients with ARDS. We hypothesize that treatment with iCO will reduce the severity of ARDS as measured by LIS over the first 7 days of the trial, as well as other physiologic measures of lung injury, including PaO₂/FiO₂, OI, and Vd/Vt. We hypothesize that treatment with iCO will reduce non-pulmonary organ failure in patients with ARDS as measured by the SOFA score.

Additional secondary endpoints will examine the effects of iCO versus placebo on biomarkers of mitochondrial dysfunction, inflammasome activation, and lipid mediators in patients with ARDS.

- Autophagy markers (eg. LC3B)
- Inflammasome-dependent cytokines (eg. IL-18)
- Lipid mediators (LM) and specialized pro-resolving mediators (SPMs)
- Mitochondrial quality control biomarkers (eg. Pink1, Wipi1)
- Biomarkers of inflammation (eg. IL-6, IL-8, IL-10, IL-1Ra)
- To enhance the biologic analytic power, samples from 12 subjects enrolled in a similar, already completed study will be similarly analyzed for these biomarkers, as well as in more extensive biologic 'omics profiling that will permit more detailed analyses of these pathways in correlation with clinical data.

Hypothesis: We hypothesize that, compared to placebo, low dose iCO will reduce mitochondrial dysfunction, attenuate inflammasome activation, and promote resolution of inflammation in patients with ARDS. Furthermore, we hypothesize that modulation of these pathways will predict improvements in the clinical outcomes of our Phase II trial.

- **Exploratory Endpoints:**

- Ventilator-free days at day 28
- ICU-free days at day 28
- Hospital-free days at day 60
- Hospital mortality to day 28 and 60

Focused Safety Analysis:

The incidence of elevation in plasma COHb \geq 10% measured on study days 1-3 and pre-specified administration-associated adverse events (**Section 7.1.8**) and serious adverse events (**Section 9.7**).

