D - CXRs done for clinical purposes will be reviewed on days 1-5. If the subject is extubated during days 1-5, a chest X-ray will be ordered by the study team the day following extubation, if not ordered by the clinical team.

E - Record clinically available creatinine, platelets, bilirubin, SBP and vasopressor use

F - Gathered on day 28 or on discharge date

G - Daily on days of study drug administration

H - AEs will be captured until study day 7

I - Obtained from discarded biobank (site specific) if available

J - Microbiological results recorded as they become available

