4.5 SECONDARY ENDPOINTS

The secondary endpoints will examine the effects of iCO versus placebo on the following outcomes:

- Lung Injury Score (LIS) on days 1-5, and 7
- $\text{PaO}_2/\text{FiO}_2$ ratio on days 1-5, and 7
- Oxygenation Index (OI) on days 1-5, and 7
- Dead Space Fraction (Vd/Vt) on days 1-3, and 7
- Sequential Organ Failure Assessment (SOFA) score on days 1-5, 7, 14, 28

Additional secondary endpoints will examine the effects of iCO versus placebo on biomarkers of mitochondrial dysfunction, inflammasome activation, and lipid mediators in patients with ARDS.

- Autophagy markers (eg. LC3B)
- Inflammasome-dependent cytokines (eg. IL-18)
- Lipid mediators (LM) and specialized pro-resolving mediators (SPMs)
- Mitochondrial quality control biomarkers (eg. Pink1, Wipi1)
- Biomarkers of inflammation (eg. IL-6, IL-8, IL-10, IL-1Ra)
- To enhance the biologic analytic power, samples from 12 subjects enrolled in a similar, already completed study will be similarly analyzed for these biomarkers, as well as in more extensive biologic 'omics profiling that will permit more detailed analyses of these pathways in correlation with clinical data.

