9 STUDY ASSESSMENTS AND PROCEDURES

9.1 DESCRIPTION OF STUDY PROCEDURES

Study assessments described below will be done according to the **Time-Events Schedule** in **Section 1.3**.

Vital Signs: Heart rate (beats/min), systemic systolic, diastolic, mean arterial blood pressure (mm Hg), and body temperature (°C), will be recorded in the eCRF.

Central Venous Pressure (CVP): CVP will be recorded if available.

Ventilator Parameters: The following settings will be recorded:

- a) Mode of ventilation
- b) FiO₂ and PEEP
- c) Tidal volume, Respiratory rate (set rate and total rate), Minute ventilation, Inspiratory flow rate
- d) Peak pressure, Plateau pressure, Compliance, and Mean airway pressure. If on a pressure-cycling mode, peak pressure during inspiration will be assumed to be the plateau pressure.
- e) Pressure during inspiration if on a pressure targeted mode (PSV, PCV, etc)

EKG: A 12 lead EKG will be performed and reviewed by a study investigator. The EKG will also be officially read

locally at each site.

Chest X-ray (CXR): The baseline frontal CXR will be reviewed by two study physician investigators to determine study eligibility. Study physician investigators blinded to treatment allocation will review and perform the assessment for the Lung Injury Score (LIS). All 4 lung quadrants will be assessed for infiltrates and pneumothoraces. If the subject is extubated on days 1-5, the study team will order a chest X-ray the day following extubation, if not ordered by the clinical team. Chest X-rays will also be ordered by the study team for endpoint analysis on Day 7, if not ordered by the clinical team.

Lung Injury Score (LIS): The lung injury score will be calculated based on the chest x-ray assessment, PaO₂, FiO₂, PEEP, and ventilator compliance measurement as described in **Appendix E1**.

Oxygenation Index (OI): The OI will be calculated based on the PaO₂, FiO₂, and mean airway pressure obtained from the ventilator parameters.

APACHE II Score: The APACHE II consists of 12 physiological variables, age, and underlying health. The score will be calculated based on the worst values in the 24 hours prior to randomization. Calculation variables are described in **Appendix E2**.

Sequential Organ Failure Assessment (SOFA): The SOFA score will be calculated based on the worst values recorded in the past 24 hours. Calculation variables are described in **Appendix E3**.

- a) Worst PaO₂/FiO₂ for that date

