- b) Worst creatinine (or urine output), bilirubin, and platelet count for that date
- c) Worst Glasgow Coma Scale for that date
- d) Vasopressor use and maximal dose for that date

Glasgow Coma Scale (GCS): The GCS is a determination of the best eye opening, motor, and verbal responses at any given time. The GCS is documented by the clinical team as part of routine ICU nursing assessment. If not available, the GCS will be assessed by the study staff as described in **Appendix E4**.

Richmond Agitation Scale (RASS): RASS is a scale used to measure the agitation or sedation level of a patient. RASS scoring is documented by the clinical team as part of routine ICU nursing assessment. If not available, the RASS will be assessed by the study staff as described in **Appendix E5**.

Blood gas analysis: The following values will be recorded from the arterial blood gas (ABG) results: pH, PCO₂, PO₂, and base excess or deficit. ABG is required for baseline assessment. If no ABG is available on subsequent days, record blood gas analysis results from the venous blood gas (VBG).

ScvO₂: ScvO₂ will be recorded if available.

Vasopressors and Inotropes Review: The following vasopressors/inotropes will be recorded in the study eCRFs. (epinephrine, norepinephrine, phenylephrine, vasopressin, dopamine, dobutamine, phosphodiesterase inhibitors, including dose).

Fluid Intake/Output: Fluid intake and output (most recent 24 hour value) or mean hourly value for most recently available period. Diuretic administration will also be recorded if applicable.

Renal replacement therapy status: Renal replacement therapy status within the last 24 hours will be recorded.

Concomitant Medications Review: The following medications will be recorded in the study eCRFs: aspirin,

angiotensin converting enzyme inhibitors (ACEIs), steroids, neuromuscular blockade, inhaled NO or prostaglandins.

Microbiological Results: Microbiological results will be recorded in the eCRF when ordered for clinical purposes.

- a) Blood cultures
- b) Urine cultures
- c) Sputum cultures
- d) BAL cultures
- e) CSF cultures if available
- f) Stool
- g) Other

Vital Status: Vital status will be assessed at Days 28, 60, and 6 months. Subjects who have been discharged from the hospital will be contacted by phone. Additional information will be collected on discharge status, ventilator status, and vasopressor status at Days 28 and 60.

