10.4.3 ANALYSIS OF THE SECONDARY AND EXPLORATORY ENDPOINTS

LIS, PaO₂/FiO₂, oxygenation index (OI), dead space fraction (Vd/Vt), and SOFA will be analyzed using repeated measures analysis of covariance (ANCOVA) to assess the effects of treatment, time, and the interaction between time and treatment, while incorporating between-patient variation in baseline measurements and important covariates including severity of ARDS (SAS PROC MIXED). Interaction contrasts will include polynomial trends

across time, focusing on a linear trend suggesting improvement and a quadratic trend suggesting that improvement is leveling off. As part of our analysis, we will also include the interaction between treatment and ARDS severity in the model. Because the study is not powered for the interaction between treatment and severity of ARDS, this test will be exploratory. We will also perform post-hoc analyses within each severity group to generate hypotheses for future study. For analysis of secondary endpoints, we will compare biological outcomes between treatment arms using the Mann-Whitney U or t-test for numerical endpoints and either χ^2 or Fisher's exact test for categorical outcomes.

Based on our prior work^{3,169}, the SD of the log-IL-18 is approximately 0.7. With 16 subjects in the placebo arm and 16 in the iCO arm, we will have > 80% power ($\alpha = 0.05$) to detect a difference in IL-18 levels of 0.5 log which corresponds to a 1.65-fold difference in plasma IL-18.

Based on an interim analysis of Cohort 1 in our Phase I trial, we will also have >80% power to detect a difference in a number of LM and SPMs including PGD₂, PGE₂, PGF_{2 α} , TXB₂, RvD2, and Mar1. Briefly, for multivariate statistical analysis, partial least square discriminant analysis (PLS-DA) will be performed as we have done previously¹⁷⁰. As we are testing multiple secondary and exploratory endpoints, a conservative 1% α level (ie. $p < 0.01$) will be used to accept statistical significance.

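### The non-pulmonary organ failure hypothesis is tested with a SOFA score that includes PaO2/FiO2, so an effect on oxygenation alone would count as support for it

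*Combined protocol and SAP*

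**What the plan says.** The synopsis (Section 1.1) treats lung injury and non-pulmonary organ failure as two separate targets. Section 10.1 gives each its own measures. LIS, PaO2/FiO2, OI and Vd/Vt serve lung injury. For the other target it says: "We hypothesize that treatment with iCO will reduce non-pulmonary organ failure in patients with ARDS as measured by the SOFA score".

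Section 4.5 lists the endpoint as "Sequential Organ Failure Assessment (SOFA) score on days 1-5, 7, 14, 28", with no qualifier.

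Section 9.1 gives four groups of inputs to the score:
- "Worst PaO₂/FiO₂ for that date"
- "Worst creatinine (or urine output), bilirubin, and platelet count for that date"
- "Worst Glasgow Coma Scale for that date"
- "Vasopressor use and maximal dose for that date"

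Footnote E to the SOFA row of the Time-Events Schedule (Section 1.3) says: "Record clinically available creatinine, platelets, bilirubin, SBP and vasopressor use".

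Section 10.4.3 places SOFA in a list of outcomes that share one model: "dead space fraction (Vd/Vt), and SOFA will be analyzed using repeated measures analysis of covariance (ANCOVA". It sets a 1% significance level for secondary and exploratory endpoints.

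**The concern.** The hypothesis concerns organs other than the lung, but the first input to the score is a lung measurement. The same measurement is a secondary endpoint in its own right and feeds both LIS and OI. Nothing in the text supplied takes it out of SOFA or plans to report the items separately.

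If iCO improved oxygenation and nothing else, the plan as written could report that result twice: once as less lung injury, and again as less non-pulmonary organ failure. The second statement would not follow from the data. The reverse also holds: a lung-item change in the other direction would hide a real non-pulmonary benefit.

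**Working it through.** **1. Hypothesis against measure.** Section 10.1 asks about non-pulmonary organ failure. Section 9.1 builds SOFA from PaO2/FiO2, creatinine or urine output, bilirubin, platelets, GCS and vasopressor use. Section 10.4.3 models the result as one variable. No section supplied defines a version without PaO2/FiO2.

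**2. What passes through.** For any scored day:

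total SOFA effect = lung-item effect (L) + non-pulmonary effect (N)

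With N = 0, the total effect equals L. None of it is removed before the test.

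**3. Illustrative size.** There is no figure in the plan to reproduce, because Table 5 gives neither an SD nor a detectable difference for SOFA. Only the arm size (16, Section 10.2) and the 1% level (Section 10.4.3) come from the documents; the 5% level is shown for comparison. The SD and L are assumptions. The calculation is a two-sided two-sample t-test at a single time point, with N = 0:

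- degrees of freedom = 2 × 16 − 2 = 30
- noncentrality = (L / SD) × √(16/2)
- for SD 3 and L = 1: (1/3) × 2.828 = 0.943

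The chance of a significant total SOFA difference with no non-pulmonary effect is:

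| Assumed SD | Assumed L (points) | At 1% | At 5% |
|---|---|---|---|
| 2 | 0.5 | 2.9% | 10.5% |
| 2 | 1.0 | 10.8% | 27.8% |
| 2 | 1.5 | 28.4% | 53.7% |
| 3 | 0.5 | 1.8% | 7.4% |
| 3 | 1.0 | 4.6% | 15.0% |
| 3 | 1.5 | 10.8% | 27.8% |
| 4 | 0.5 | 1.4% | 6.4% |
| 4 | 1.0 | 2.9% | 10.5% |
| 4 | 1.5 | 5.8% | 17.7% |

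The ranges are 1.4% to 28% at the 1% level and 6% to 54% at the 5% level. The planned repeated-measures model would give other figures, but the pass-through in step 2 would be the same.

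**4. Source of the lung item over time.** From the Time-Events Schedule (R = required, A = only if available):

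| Row | Days 1–3 | Days 4–5 | Day 7 | Day 14 | Day 28 |
|---|---|---|---|---|---|
| SOFA | R | R | R | R | R |
| Blood gas | R | A | R | A | none |
| SpO2 | R | R | R | A | none |
| Ventilator parameters | R | R | R | R | none |
| CBC | R | A | A | A | A |
| Basic metabolic panel | A | A | A | A | A |
| Bilirubin | R | R | R | R | R |
| GCS | R | R | R | R | R |

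The lung item therefore has no assured source on Day 14 and no listed source on Day 28. The rule in Section 7.1.4 for estimating PaO2/FiO2 from SpO2 applies only while the subject is intubated with SpO2 no higher than 97%. Platelets and creatinine also depend on availability on Days 14 and 28.

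**The case against.** **Unseen sources.** Section 9.1 refers the SOFA calculation to Appendix E3, and Section 10.4.1 (General Approach) refers analysis detail to a separate Statistical Analysis Plan. Neither was in the text supplied. This limit stands. It is not evidence that a lung-excluded score exists, and the protocol text as it reads says otherwise.

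**A lung-only effect would be visible.** PaO2/FiO2, OI and LIS are reported on Days 1–5 and 7, so a reader could suspect the cause of a SOFA difference. That is fair, but suspicion is not separation: no planned analysis isolates the non-pulmonary part.

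**The strict alpha.** A 1% level makes a chance finding less likely. It does not alter what is measured.

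**A simpler remedy.** Rewording the hypothesis to overall organ failure would also remove the mismatch. It would, however, give up the non-pulmonary claim that the synopsis names as a separate target.

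**Stronger readings that the documents do not support.**
- A reader might take footnote E as proof that the lung item is dropped, or that the score changes composition between days. It attaches to the whole SOFA row, so it shows no difference between days. It also leaves out GCS, which Section 9.1 includes. It is a note on data capture and does not define the score in either direction.
- A reader might infer that Day 28 SOFA has five organs against six earlier, and so falls artificially. SOFA is marked as required on Day 28, no passage says a missing item is scored as zero, and other inputs have gaps too. Any loss built into the schedule applies to both arms and is not by itself a treatment effect.
- A reader might infer that the five non-pulmonary items are fully collected. The table in step 4 shows they are not.

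**Conclusion.** The mismatch is real on the text supplied: the measure named for non-pulmonary organ failure contains a pulmonary item, and nothing planned takes it out. A difference in total SOFA could not be attributed to the other organs.

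How often this would mislead cannot be derived from the documents. The illustrative 4.6% at the 1% level (range 1.4% to 28%) rests entirely on the assumed SD and lung-item effect. These are not false-positive rates for total SOFA, which truly differs in those scenarios. They are the chance that a lung-only effect is significant in the test assigned to the non-pulmonary hypothesis.

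The lack of a clear source for the lung item on Days 14 and 28 is a lesser, related point. The endpoint is secondary, and the primary mtDNA conclusion is unaffected. The change should be made before analysis, so that no choice between SOFA versions is made after the data are seen.

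**What to change.** - In Sections 4.5, 10.1 and 10.4.3, name non-pulmonary SOFA (the cardiovascular, renal, hepatic, coagulation and neurological items, without PaO2/FiO2) as the measure for this hypothesis. Carry the same wording into the endpoint lists in Sections 1.1 and 2.
- Report total SOFA and the respiratory item separately. State what supplies the respiratory item on Days 14 and 28 if total SOFA is reported then.
- Align footnote E with the inputs listed in Section 9.1.
- Check Appendix E3 and the separate SAP. If either already excludes the lung item, bring the protocol text into line with it.

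The cost is wording. The proposal needs no extra patients or procedures. The lung-excluded score is less directly comparable with published total-SOFA results, which the separate report of total SOFA largely covers. The gaps in creatinine and platelets remain, as they do for total SOFA.
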